7.4 INTERIM ANALYSES

As the trial will be conducted as a double-blind trial, an independent external DMC will be established to periodically assess the progress of the clinical trial, including un-blinded safety and efficacy assessments.

A decision as to whether or not the trial is expanded into a Phase III trial will be made by the DMC at the time-point of the primary PFS analysis for this Phase II trial. In order to limit knowledge of the criterion for expansion potentially having an impact on the future conduct of the trial, the criterion for expansion will be pre-defined in the DMC charter (prior to trial initiation) and not this protocol. This analysis will be conducted after approximately 40 PFS events (predicted to occur after 30 months). Note the exception to this as specified in [Section 7.3](#).

If the criterion for the seamless option is met and the trial is expanded into a Phase III trial then formal hypothesis testing (refer to [Section 7.2](#)) will be performed with suitable control of the overall type I error rate. In this situation the primary PFS analysis at the end of Phase II will be considered as an interim analysis. Under the null hypothesis the probability of meeting the criterion for seamless expansion and subsequently achieving a one-sided p-value of <0.0249 (see details below) is 0.0028. Analysis time-points along with alpha-spending and control are presented in [Figure 7.4: 1](#) below.

[figure not shown]

Figure 7.4: 1 Planned testing strategy

If expanded, some (technical) alpha-level of 0.0001 one-sided (see [Figure 7.4: 1](#)) will be spent at the time-point of the Phase II primary PFS analysis to adjust for the unblinded interim look by the DMC. If the alpha-boundaries are crossed at this interim analysis time point there are no plans to stop the trial early. A group sequential design user defined alpha-spending function has been used to calculate the final level leading to a nominal level of approximately 0.0249 (ADDPLAN v6.1.1). The nominal level available will be recalculated based on the actual information fraction at the interim, but keeping the alpha spent at 0.0001 for the interim look.

In order to integrate the secondary endpoint of OS into the confirmatory testing strategy in a hierarchical manner, the same alpha-spending function as used for the primary PFS endpoint will be applied. Note that although OS is integrated into the testing strategy it will not be powered for OS and a significant OS benefit is not necessarily expected. The study is considered positive if the primary hypothesis on PFS can be rejected.

Further details will be provided in a protocol amendment if the seamless option is met and the trial is expanded.

7.5 HANDLING OF MISSING DATA

In general missing efficacy data will not be imputed and all reasonable efforts will be taken during the study to obtain such data. Patients with unknown vital status, missing tumour imaging data and missing PRO assessments will be censored for time to event analyses as detailed below.

[Table 7.5: 1](#) describes how patients will be classified for the analysis of PFS. Sensitivity analyses will examine the effect of using alternative rules.

Table 7.5: 1 Derivation rules for PFS

Situation	Outcome	Date of outcome
No baseline radiological assessment		
Death on or before the second planned radiological assessment	Event	Date of death
Alive or death after second radiological assessment	Censored	Date of randomisation
Without post-baseline radiological assessments		
Vital status is unknown or known to be alive	Censored	Date of randomisation
Death prior or on the second planned radiological assessment	Event	Date of death
Death beyond the second planned radiological assessment	Censored	Date of randomisation
With baseline and post-baseline radiological assessments BUT no other anti-cancer therapy		

Table 7.5: 1 Derivation rules for PFS (cont'd)

Alive and not progressed, no more than one consecutively missed radiological assessments	Censored	Date of last radiological assessment
Alive and not progressed, two or more consecutively missed radiological assessments	Censored	Date of last radiological assessment prior to missed radiological assessments
Progressed, zero or one missed radiological assessment prior to progression	Event	Date of radiological assessment of progression
Progressed, but two or more consecutively missed radiological assessments prior to progression	Censored	Date of last radiological assessment prior to missed assessment
Death but no progression, zero or one missed radiological assessment prior to death	Event	Date of death
Death without progression, but two or more consecutively missed radiological assessments prior to death	Censored	Date of last radiological assessment prior to missed assessments
Initiation of subsequent anti-cancer therapy		
Subsequent anti-cancer therapy started before progression or death	Censored	Date of last radiological assessment before subsequent anti-cancer therapy
No baseline and/or post-baseline imaging and subsequent-anti cancer therapy started prior to a death	Censored	Date of randomisation

For endpoints related to OR and DC the rules defined above, where applicable, will be followed.

[Table 7.5: 2](#) describes how patients will be classified for the analysis of death. Patients will be censored at the date of last contact if the investigator is no longer able to contact a patient or caregiver, and vital status cannot be determined otherwise, provided that no other information indicates that the patient was near death at that point.

Table 7.5: 2 Derivation rules for OS

Status at time of analysis	Outcome	Date of outcome
Death and the date of death is known	Event	Date of death
Death and date of death is unknown	Event	Date of last contact when the patient is known to be alive + 1 day
Alive	Censored	Date of last contact when the patient is known to be alive
Unknown	Censored	Date of last contact when the patient is known to be alive

7.6 RANDOMISATION

Patients will be randomised in blocks to double-blind treatment with a 1:1 ratio (xentuzumab in combination with everolimus and exemestane: everolimus and exemestane alone).

Randomisation will be stratified by the following factors:

- Presence of baseline bone-only metastases (Yes, No)
- Prior CDK4/6 inhibitor treatment (Yes/No)

BI will arrange for the packaging and labelling of trial medication. The randomisation list will be generated using a validated system, which involves a pseudo-random number generator so that the resulting treatment will be both reproducible and non-predictable.

The block size will be documented in the CTR. Access to the codes will be controlled and documented.

7.7 DETERMINATION OF SAMPLE SIZE

For the primary endpoint of PFS, it is assumed that xentuzumab in combination with everolimus and exemestane will increase the median from 9.9 months ([R16-0802](#)) in the everolimus and exemestane alone group to 19.8 months. Assuming an exponential distribution, this is equivalent to a reduction in the risk for progression of disease or death of 50%, corresponding to an underlying hazard ratio (HR) of 0.50. With 80 eligible patients randomised over a 15 month period, 40 PFS events are predicted to be reached on average around 30 months after the first patient is randomised. This assumes approximately 20% of patients randomised will either drop out of the trial without evidence of disease progression or be assessed as non-PD by independent assessment when the investigator assigned disease progression. If this proportion differs significantly from the 20% assumed then the number of patients randomised may be increased in order to observe 40 PFS events in a timely manner, but the number of patients randomised will not exceed 100 patients.

[Table 7.7: 1](#) shows the probability of observing various HR thresholds for different underlying (true) HR values and accrued PFS events.

Table 7.7: 1 Probability (%) of observed HR for a range of underlying HRs and PFS event numbers

PFS Events	Underlying (True) HR	Probability ¹ observing HR			
		≤0.50	≤0.60	≤0.75	>0.75
50	HR=1.00	0.7%	3.5%	15.5%	84.5%
40		1.4%	5.3%	18.1%	81.9%
30		2.9%	8.1%	21.5%	78.5%
50	HR=0.60	26.0%	50.0%	78.5%	21.5%
40		28.2%	50.0%	76.0%	24.0%
30		30.9%	50.0%	72.9%	27.1%
50	HR=0.50	50.0%	74.0%	92.4%	7.6%
40		50.0%	71.8%	90.0%	10.0%
30		50.0%	69.1%	86.7%	13.3%
50	HR=0.40	78.5%	92.4%	98.7%	1.3%
40		76.0%	90.0%	97.7%	2.3%
30		72.9%	86.7%	95.7%	4.3%

¹ Calculated using the approximate normal distribution of the estimated log HR

With 40 PFS events, if the underlying HR is 0.50, the chance of observing a treatment effect with HR of ≤0.60 is 71.8%, while the chance of observing a treatment effect with HR of ≤0.75 is 90.0%. Also, if the underlying HR is 1.0, the chance of observing a treatment effect with HR of ≤0.60 is 5.3%, while the chance of observing a treatment effect with HR of ≤0.75 is 18.1%. If the PFS events were increased from 40 to 50, the probability of observing a treatment effect with HR of ≤0.60 is increased by 2.2% (from 71.8% to 74.0%) for an underlying HR of 0.50, similarly for a treatment effect with HR of ≤0.75 the increase in probability is 2.4%.

Probabilities of 71.8 or 90%, respectively, based on 40 PFS events and an underlying HR of 0.50 is considered high enough to provide evidence that will allow an informed decision to be made in terms of the next stages of development.

The trial includes a seamless option for the expansion of the ongoing Phase II trial into a Phase III trial provided the predefined criterion (to be defined in the DMC charter) is met after 40 PFS events have been observed.

If the trial meets the criterion for expansion a further 220 patients will be randomised, so 300 patients in total, 150 per treatment arm. Primary analysis would be planned after approximately 176 PFS events, 40 from the primary Phase II analysis time-point plus an additional 136 events after this time-point. With 220 additional patients randomised into the expansion part at a constant rate over a 14 month period, 176 PFS events are predicted to be reached on average around 64 months after the first patient is randomised into the Phase II trial. This includes a 4-month gap between the Phase II results and starting the expanded trial. It is expected that approximately 20% of patients randomised will either drop out of the trial without evidence of disease progression or be assessed as non-PD by independent assessment when the investigator assigned disease progression. This has been accounted for with the planned total of 300 patients to be randomised. Note as for the Phase II part if the drop-out rate differs significantly from 20% the total number of patients randomised may need to be increased from 300, but will not exceed 375.

The patient numbers have been chosen to provide a sufficient amount of efficacy and safety data for submission. A standalone Phase III trial, with an assumed HR of 0.60 and 176 events, would achieve an overall power of at least 90% controlling the overall type I error at 2.5% (one-sided). Also, when considering solely the expansion part with 136 events it is ensured that based on an assumed HR for the expansion part of 0.60 the respective one-sided (second stage) p-value would be less than 0.05 in 90% of the cases. Thereby it is assumed that the event size for the second stage is sufficiently large to allow for informed decision making on homogeneity across the two trial parts in the case of the seamless option being met.

Note that although OS is included in the confirmatory testing strategy, if the trial is expanded, no power calculations have been performed as a significant OS benefit is not anticipated, due to unequal post-progression treatment being expected to obscure the effect of xentuzumab relative to placebo.

8 INFORMED CONSENT, TRIAL RECORDS, DATA PROTECTION, PUBLICATION POLICY, AND ADMINISTRATIVE STRUCTURE

The trial will be carried out in compliance with the protocol, the ethical principles laid down in the Declaration of Helsinki, in accordance with the ICH Harmonized Tripartite Guideline for Good Clinical Practice (GCP), relevant BI Standard Operating Procedures (SOPs), European Directive 2001/20/EC and/or the EU regulation 536/2014 once coming into force, and other relevant regulations.

Standard medical care (prophylactic, diagnostic and therapeutic procedures) remains the responsibility of the treating physician of the patient.

The investigator will inform the sponsor immediately of any urgent safety measures taken to protect the trial patients against any immediate hazard, as well as of any serious breaches of the protocol or of ICH GCP.

The Boehringer Ingelheim transparency and publication policy can be found on the following web page: trials.boehringer-ingelheim.com. The rights of the investigator and of the sponsor with regard to publication of the results of this trial are described in the investigator contract. As a rule, no trial results should be published prior to finalization of the Clinical Trial Report unless defined otherwise in the publication strategy.

The certificate of insurance cover is made available to the investigator and the patients, and is stored in the ISF.

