2. TRIAL OBJECTIVES AND ENDPOINTS

2.1 MAIN OBJECTIVES, PRIMARY AND SECONDARY ENDPOINTS

2.1.1 Main objectives

This double-blind, placebo-controlled, randomised Phase II trial will be performed in female patients with HR+/HER2- advanced or metastatic breast cancer and non- visceral disease. The main objective of the trial is to assess the efficacy of xentuzumab in combination with everolimus and exemestane over everolimus and exemestane in this patient population. Efficacy will be assessed by determining whether or not the criterion for expanding the trial seamlessly into a Phase III trial is met. If the seamless option is met the trial will be expanded into a confirmatory Phase III trial with formal superiority hypothesis testing. If the seamless option is not met, the observed results will be evaluated in an explorative manner to see if they are sufficient for further development of this compound in this indication.

All imaging-related endpoints will be both independently assessed (in a blinded fashion) and investigator assessed according to RECIST 1.1 (see [Appendix 10.4](#)). The data from the independent assessments will be considered primary, with investigator assessment data as supportive.

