The primary objective of this Phase II trial, that xentuzumab in combination with everolimus and exemestane prolongs PFS, will be addressed by assessing whether or not the criterion for the seamless option has been met. If the seamless option is not met, the observed results will be evaluated in an explorative manner to see if they are sufficient for further development of this compound in this indication (e.g. via a separate Phase III trial). If the seamless option is met then expansion into a Phase III trial will allow for formal hypothesis testing via a one-sided test at an alpha level determined by a number of factors (refer to [Section 7.4](#)), controlling for the overall type I error rate of 0.025 (one-sided). The hypothesis testing will be supported by the hazard ratio and corresponding 95% CI from a stratified Cox proportional hazards model to describe the magnitude and precision of treatment effects.

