7.3 PLANNED ANALYSES

The primary analysis of PFS for this Phase II trial will take place when approximately 40 patients have had disease progression (assessed by independent review) or died. The time point of reaching 40 events will be estimated using investigator assessed events and the discrepancy rates observed between independent and investigator data during the trial. The estimation of this time point is likely to lead to some deviation, though relatively small, from the planned 40 independent assessed events. Based on assumed median PFS times (refer to [Section 7.7](#)), the analysis is expected to take place 15 months after the last patient has been randomised. This analysis will be performed by the DMC.

If the criterion for the seamless option is met then the trial will be expanded into a confirmatory Phase III trial and remain double-blind. If the criterion is not met then the database will be unblinded and a clinical trial report (CTR) written, including the evaluations of the primary, secondary and further endpoints. Note that based on these results it is still possible that clinical development in this indication will be continued (e.g. via a separate Phase III trial), in addition patients randomised into this Phase II trial will have further data collected and reported upon, beyond the unblinding time-point. Blinded dummy treatment group assignments will be used in the study database whilst the trial remains blinded. [Section 4.1.6](#) provides further details on the blinding and procedures for unblinding.

An exception to the above plan will occur if the proportion of randomised patients dropping out of the trial without evidence of disease progression, becomes so high that reaching 40 PFS events is either not possible, or has not been met 20 months after the last patient has been randomised. In such an unlikely scenario no DMC analysis will be performed and therefore

the criterion for seamless expansion will not have been met. In this situation the database will be unblinded and a CTR written, including the evaluations of the primary, secondary and further endpoints.

Imaging related endpoints will be both independently assessed and investigator assessed according to RECIST 1.1. The data from the independent assessments will be considered primary, with investigator assessment data as supportive.

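### Should Section 7.7 justify 40 and 176 events by the probability of meeting the expansion criterion?

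*Protocol*

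**What the plan says.** Two parts of the protocol have to be read together.

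**What answers the objective.** Section 2.1.1 says: "Efficacy will be assessed by determining whether or not the criterion for expanding the trial seamlessly into a Phase III trial is met". Section 7.2 repeats that the Phase II primary objective "will be addressed by assessing whether or not the criterion for the seamless option has been met". The criterion is a threshold on the observed HR at the primary PFS analysis, and Section 7.4 explains that "the criterion for expansion will be pre-defined in the DMC charter (prior to trial initiation) and not this protocol", so that knowledge of it cannot affect the conduct of the trial. The same section gives one figure for the combined rule: the null probability of expanding and then "achieving a one-sided p-value of <0.0249 (see details below) is 0.0028".

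**What supports the numbers.** Section 7.7 relies on Table 7.7: 1 and concludes: "Probabilities of 71.8 or 90%, respectively, based on 40 PFS events and an underlying HR of 0.50 is considered high enough". It compares 40 with 50 events ("If the PFS events were increased from 40 to 50, the probability of observing a treatment effect with HR of" at most 0.60 rises by 2.2 points, and for 0.75 by 2.4 points). For the expanded trial it says: "A standalone Phase III trial, with an assumed HR of 0.60 and 176 events, would achieve an overall power of at least 90" per cent. It adds that the 136 new events alone would give a one-sided p-value below 0.05 in 90% of cases at HR 0.60.

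Section 7.3 says that if the criterion is missed, "it is still possible that clinical development in this indication will be continued (e.g. via a separate Phase III trial").

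**The concern.** If the main objective is answered by a go/no-go rule, the sizing section would be expected to say how often that rule gives a go when the drug works. Section 7.7 does not. The 71.8% and 90% refer to thresholds of 0.60 and 0.75, and the figure of at least 90% is for a trial with no go step.

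The 0.0028 in Section 7.4 suggests a stricter threshold than either. A reader could leave Section 7.7 believing that the decision step has 70% to 90% sensitivity at the design HR of 0.50, when the seamless route would be taken only about half the time. The comparison of 40 with 50 events would also look misplaced: with a cut-off equal to the true HR, the chance of a go is 50% whatever the number of events. At stake would be a sponsor, or an ethics committee, misjudging how likely the trial is to expand.

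**Working it through.** **Inputs (Protocol Sections 7.2, 7.4, 7.6 and 7.7).** 1:1 allocation; 40 events at the Phase II analysis and 176 in total (40 + 136); final one-sided level 0.0249, so critical value 1.9617; null joint probability 0.0028; true HRs of 0.50 and 0.60. The log HR is treated as normal with variance 4/d for d events, as in the footnote to Table 7.7: 1.

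**1. The plan's own figures.** P(observed HR ≤ c) = Φ[√(d/4) × ln(c/HR)]. With d = 40, √10 = 3.162.

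- c = 0.60, HR 0.50: Φ(3.162 × 0.1823) = Φ(0.577) = 71.8%.
- c = 0.75, HR 0.50: Φ(3.162 × 0.4055) = Φ(1.282) = 90.0%.
- Power at 176 events, HR 0.60, one-sided 0.025: Φ(6.633 × 0.5108 − 1.960) = Φ(1.429) = 92.3%, against at least 90% stated.
- 136 events, HR 0.60, one-sided 0.05: Φ(5.831 × 0.5108 − 1.645) = Φ(1.334) = 90.9%, against 90% stated.

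All entries in the ≤0.50, ≤0.60 and ≤0.75 columns of the table reproduce.

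**2. The cut-off implied by 0.0028.** If the final test uses all 176 events, the two test statistics are bivariate normal with correlation √(40/176) = 0.477. The null probability of a go at cut-off c followed by final significance is:

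| c | joint null probability |
|---|---|
| 0.50 | 0.00285 |
| 0.60 | 0.00716 |
| 0.75 | 0.01470 |

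Solving for 0.0028 gives c = 0.499 (0.497 to 0.500 over the rounding range 0.00275 to 0.00285). On this reading, neither threshold discussed in the text is the criterion.

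**3. Chance of a go at c = 0.50 and 40 events.**

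- True HR 0.50: Φ(0) = 50.0%. Go and final success: 50.0%.
- True HR 0.60: Φ(3.162 × ln(0.50/0.60)) = Φ(−0.577) = 28.2%. Go and final success: 27.8%.
- True HR 1.00: Φ(3.162 × ln 0.50) = Φ(−2.192) = 1.4%.

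The three go probabilities are the 40-event entries of the ≤0.50 column of Table 7.7: 1. Adding the final test changes little: success given expansion at HR 0.60 is 27.8/28.2 = 98.6%.

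**4. Does the number of events matter for the go decision?** At c = 0.50 and true HR 0.50 the chance of a go is 50.0% at 30, 40 and 50 events. The null go rate falls from 2.9% to 1.4% to 0.7%. More events therefore protect against a false go, and they do bear on the decision.

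**5. Sensitivity to the reading of 0.0028.** Suppose the 0.0249 test used only the 136 new events, independently of the first 40. Then P(go under the null) = 0.0028/0.0249 = 0.1124, and c = exp(Φ⁻¹(0.1124)/3.162) = 0.68. The chance of a go would be Φ(3.162 × ln(0.681/0.50)) = 84% at HR 0.50 and Φ(3.162 × ln(0.681/0.60)) = 66% at HR 0.60. The group-sequential level and the 176-event analysis favour the cumulative reading.

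**The case for a change.** The strongest case for a change is that the protocol itself makes the expansion criterion the answer to its objective, so its operating characteristics under the alternative belong with the sample size. Concealment is a weak defence when the published 0.0028 lets a reader recover a cut-off of about 0.50. A cross-reference to the DMC charter would cost one sentence.

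Part of this stands. Section 7.7 does not identify any probability of expansion under the alternative, and a reader in a hurry could take 71.8% or 90% for one.

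The rest does not carry through. The sentence with those figures concerns a decision on later development. The seamless option comes up only afterwards and is referred to the charter. Under Sections 7.2 and 7.3 that wider decision remains open when the criterion is missed, and thresholds of 0.60 and 0.75 are relevant to it. The power figure is labelled standalone. On the likelier reading the go probabilities are already in the table; what is missing is a label that would disclose the cut-off the protocol chose to withhold. The charter is not among the documents, so it cannot be said that these figures were never set down.

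**Conclusion.** No change follows. Section 7.7 leaves out a description of the seamless route, but nothing it states is wrong and nothing in the analysis depends on what it leaves out. A strict gate, with about a 50% chance of a go at HR 0.50, 28% at HR 0.60 and 1.4% under the null, is a fair trade-off when missing the gate leads to exploratory evaluation and does not end development. Changing the justification would leave the tests, estimates, event targets and patient numbers as they are. It would also affect no pending decision: Section 1.4 reports that the Phase II analysis showed no added benefit, and SAP Section 3 covers only the scenario without expansion.

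The sizes rest on the normal approximation used in Table 7.7: 1, on exactly 40 and 176 events, and on the final test using cumulative data. With 36 to 44 events at the first analysis the implied cut-off would run from 0.487 to 0.509. Under the independent-stage reading it would be about 0.68, with go probabilities of about 84% and 66%. The conclusion is the same on either reading.
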